5.1.2 Baseline Definition

For efficacy and safety analyses presented by study visit, the main SAP defines the baseline value as "the last measurement prior to the start of study drug administration". The baseline value will differ for summaries of Hamilton Depression Rating Scale - 17item Version (HAMD-17), Clinical Global Impression of Improvement (CGI-I), Snaith-Hamilton Pleasure Scale (SHAPS), Hospital Anxiety and Depression Scale (HADS), Hamilton Anxiety Rating Scale (HAM-A), Sheehan Disability Scale (SDS), Clinical Global Impression of Severity (CGI-S),

and

presented by study visit, in which case the baseline value will be defined as the last measurement prior to or within 1 hour of the first administration of study drug. For all other efficacy and safety analyses presented by study visit, the baseline value will be defined as stated in the main SAP.

5.2 Efficacy Evaluation

5.2.1 Measurements of Treatment Compliance

As stated in the main SAP, percentage compliance to the study treatment regimen will be determined as the total dose actually taken divided by the expected dose received, multiplied by 100. The expected dose received will be calculated as (the date of last dose of study drug – the date of first dose of study drug + 1 day) x 1 capsule/day. If the date of last dose is missing or unknown, the date of last dose will instead be equal to the date of last available visit prior to Visit 7 or the date of study completion/termination, whichever is earlier. The date of the last available visit prior to Visit 2 (Baseline) and Visit 6 (Week 8)/ET (end of treatment). Any bottles dispensed on or after the date of last dose will be excluded from the calculation of total dose actually taken.

In the case of missing values, the following calculations will differ from the main SAP. If the number of capsules taken is missing, but the corresponding number of capsules dispensed and returned are not missing, then the number of capsules taken will be calculated as the number of capsules dispensed minus the number of capsules returned. If both the number of capsules returned and the number of capsules taken are missing, then it will be assumed that 0 capsules were returned and all capsules dispensed were taken. In addition, if the number of capsules dispensed is 0, then the corresponding number of capsules taken and returned will be set to 0.

Dosing compliance will be summarized using descriptive statistics, by treatment group, based on the Efficacy Population. As an exception rule, the compliance rate for subjects with ≤ 14 days exposure duration will not be calculated, as the compliance may not be calculated reliably for such short duration.

5.2.2 Sensitivity Analyses of the Primary Efficacy Endpoint

The main SAP describes the sensitivity analyses that will be performed. The Last Observation Carried Forward (LOCF) Imputation technique will be performed as follows: the last observed non-missing post-baseline value will be used to fill in missing values at Week 8, regardless of when the missing value occurred. The imputed dataset generated with the LOCF technique will be used as input data in the analysis of covariance (ANCOVA) analysis.

5.2.3 Subgroup Analyses of the Primary Efficacy Endpoint

The primary efficacy endpoint (change from baseline to Week 8 in HAMD-17 total score) will be summarized using the subgroups described in the main SAP. Additionally,

the mixed-models repeated measures (MMRM) analysis described for the primary efficacy endpoint in the main SAP will be repeated for all subgroups.

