The signature below constitutes agreement with this protocol and attachments, and provides assurance that this study will be conducted according to all stipulations of the protocol, including all statements regarding confidentiality, and according to national and local legal and regulatory requirements and applicable regulations and guidelines.

Principal Investigator:	
Address:	
Signature:	
Date:	

BTRX-335140	BlackThorn Therapeutics, Inc.
Clinical Study Protocol Amendment 7	Date: 24Jan2022

SUMMARY OF CHANGES

This section describes significant changes made in Version 8.0 of the protocol. Changes to punctuation, formatting (ie, changes in numbering, word order, location, etc.), the table of contents, and the list of abbreviations and definitions of terms are not listed in the summary of changes table (Table 1).

Section Number and Title	Description of Change	Rationale
Synopsis – Statistical Methods, Section 9 Statistical Considerations, Efficacy Analyses	Changed alpha, power, and confidence interval (CI) for efficacy analyses to reflect 2-sided alpha=0.05; power of 84% and 95% CIs	To decrease the chance of a Type I error.
Synopsis – Study Design, Schedule of Procedures and Assessments (footnotes c, h, and t), Section 3.1, Section 6.3.6, Section 7.6, Section 7.7.2, Section 7.8	Clarified wording around the Week 12 corneal specular microscopy, which should be completed for all subjects (ie, completers and early termination) unless consent is withdrawn. Also added clarification that additional ophthalmologic examinations (standard ophthalmologic exams and/or corneal specular microscopies) may be conducted at any time during the study to assess subject safety.	In the event of early termination, every attempt should be made to get a subject to come back for corneal specular microscopy at 12 weeks after the first dose of study drug. Added text to reflect potential of unscheduled ophthalmologic and/or corneal specular microscopies to assess safety
Section 3.2.2, Section 3.2.3, Section 9.3.3.2, Section 9.3.5	Moved CGI-S from an exploratory to a secondary endpoint.	Supports the secondary objectives; consistency with the SAP
Synopsis – Statistical Methods, Section 9.3.3.2	Added description for analysis of CGI-S using generalized estimating equations (GEE)	Consistency with the SAP
Synopsis – Statistical Methods, Section 9.3.3.2	Revised statistical text for secondary efficacy analyses to allow for ANCOVA as appropriate.	Clarity and consistency with the SAP

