Subjects who meet the DSM-5 diagnostic criteria for MDD and all other eligibility criteria for the study will be randomized in a 1:1 ratio to 1 of 2 treatment arms (placebo or BTRX-335140 QD) until approximately 180 subjects are randomized. Beginning at Visit 2 (Baseline), subjects will receive treatment with BTRX-335140 80 mg QD or placebo for 8 weeks. During the Safety Follow-up, all subjects will receive a telephone call (TC) from study site personnel approximately 2 weeks after discontinuation of study drug for assessment of AEs, concomitant medication usage, and C-SSRS; and at Week 12, subjects will have corneal specular microscopy performed by a study site-affiliated ophthalmologist. The overall duration in the study for each subject is expected to be approximately 14 to 16 weeks.

The Week 12 corneal specular microscopy should be completed for all subjects (ie, completers and early termination) unless consent is withdrawn. The corneal specular microscopy should be conducted approximately 12 weeks after the first dose of study drug; subjects who terminate the study early would need to plan for the corneal specular microscopy at 12 weeks after the first dose of study drug. Any exceptions are to be discussed with the medical monitor.

Additional ophthalmologic examinations (standard ophthalmologic exams and/or corneal specular microscopies) may be conducted to assess subject safety.

Details of study procedures and assessments are provided in Section 6; for details on the timings of study assessments refer to Section 7 and the Schedule of Procedures and Assessments.

Study sites will maintain, at a minimum, coronavirus disease 2019 (COVID-19) risk mitigation procedures as per regulatory and local guidelines and/or laws. Allowed modifications to the conduct of the study, in the event of site staff and/or patient restrictions due to COVID-19, are outlined in Appendix 1.

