9 STATISTICAL CONSIDERATIONS

9.1 General Considerations

Full details on the statistical methodology to be used will be included in a statistical analysis plan (SAP) to be developed prior to study unblinding.

For the purpose of all safety analyses where applicable, baseline is defined as the last measurement prior to the start of study drug administration. For efficacy analyses, baseline is defined as the arithmetic mean of pretreatment measurements ie, Screening and Baseline, prior to the first administration of study drug, or as the last measurement prior to the first administration of study drug if only single value is available.

Continuous endpoints will be summarized with n, mean, standard deviation (SD), median, minimum and maximum. In addition, change from baseline and percent change from baseline values will be calculated at each time point and summarized descriptively. For categorical endpoints, descriptive summaries will include counts and percentages.

No adjustments will be made for multiple comparisons.

All statistical comparisons will be 2-sided with alpha of 0.05.

SAS version 9.4 or higher will be used to analyze data.

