7.1.6 Multiple Comparisons/Multiplicity

The prespecified primary efficacy analysis will be conducted using a two-sided test at the α =0.05 level of significance. All other analyses will be also conducted with no adjustments for multiple comparisons.

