7.4.4 Primary Efficacy Endpoint Analysis Methods

The primary efficacy endpoint is the change from baseline to Week 8 on the HAMD-17 score. The estimand for the primary efficacy endpoint is the difference in means between treatment groups in the change of HAMD-17 scores from baseline to Week 8 for all subjects in the Efficacy population. For efficacy analyses, baseline is defined as the latest measurement prior to the first administration of study drug. The null hypothesis to be tested is that there is no difference between BTRX-335140 and placebo:

H₀:
$$\mu_A = \mu_{B_i}$$

Where μ_A and μ_B represent the mean values for BTRX-335140 and placebo, respectively. The alternate hypothesis to be tested is that the treatment group means differ:

H₁:
$$\mu_A \neq \mu_{B}$$
;

The analysis will be conducted using a mixed-models repeated measures (MMRM) with change from baseline in HAMD-17 score as the dependent variable and will include treatment group, week, and week by treatment group interaction as factors, and baseline HAMD-17 score as covariate. Variance estimation will be based on an unstructured covariance matrix. If the unstructured covariance matrix results in a lack of convergence, the heterogeneous autoregressive variance-covariance structure will be used.

The primary analysis will compare the groups at Week 8. The primary results obtained from the model will be the estimated treatment difference at Week 8. Significance will be assessed based on a two-sided test at the α =0.05 level of significance. In addition, the estimated treatment difference at Week 4 will be provided. The model-based least square (LS) means, standard errors, 95% CIs, and 2-sided p-values will be reported.

In addition, descriptive summary of HAMD-17 and each individual item will be generated by treatment group and by visit.

BlackThorn Therapeutics, Inc.	Statistical Analysis Plan
K2-MDD-201	Version 2.0; 03 June 2022

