7.4.6 Subgroup Analyses of the Primary Efficacy Endpoint

The primary efficacy endpoint (change from baseline to Week 8 in HAMD-17 total score) will be summarized using the following subgroups:

- Gender (male and female)
- Baseline HAMD-17 scores: $< 22 \text{ vs} \ge 22$
- by baseline SHAPS Total Score (14 to 56) (< median and ≥ median) and SHAPS Original Total Score (0 to 14) (< median and ≥ median).

Summaries by subgroup will only be produced if there are at least 20 subjects in the category of interest. Additional subgroup analyses may be performed post-hoc, as appropriate.

The primary endpoint (HAMD-17 total score) will also be summarized in subgroups of the Efficacy Population that include all subjects screened on or before March 16, 2020 (labeled as PreCOVID) versus the subjects screened after March 16, 2020 (labeled as PostCOVID).

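### Subgroup MMRMs of the primary endpoint give each level its own unadjusted p-value, and no visible text estimates whether the treatment effect differs between levels

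*SAP*

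**What the plan says.** Main SAP 7.4.6 plans to summarize the Week 8 change in HAMD-17 by gender, by baseline HAMD-17 (below 22 versus 22 or more), and by baseline SHAPS split at the median under each of two scorings. A category needs at least 20 subjects. A separate paragraph adds a summary for subjects screened before and after 16 March 2020.

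Addendum 5.2.3 goes further: the primary MMRM "will be repeated for all subgroups".

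Main SAP 7.4.4 defines that model. Its factors are "treatment group, week, and week by treatment group interaction as factors", with baseline HAMD-17 as covariate. Its output is stated as follows: "The model-based least square (LS) means, standard errors, 95% CIs, and 2-sided p-values will be reported".

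On error control, protocol 9.1 states "All statistical comparisons will be 2-sided with alpha of 0.05", and main SAP 7.1.6 states "All other analyses will be also conducted with no adjustments for multiple comparisons".

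No visible text in protocol 9.3.6, main SAP 7.4.6 and 7.4.8, or addendum 5.2.3 and 5.2.4 gives a treatment-by-subgroup term, a test or estimate of heterogeneity, or a caution about comparing significance between levels.

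**The concern.** One significant level and one non-significant level do not show that the effect differs between them. The plan produces up to eight within-level p-values from the four factors in the main list, and none of them measures that difference.

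This matters more here than in a trial where subgroups are a formality. The study is a proof of concept, its rationale rests largely on anhedonia, and two of the four factors are splits on an anhedonia scale. A significant result in high-SHAPS subjects and not in low-SHAPS subjects could be taken as a finding about which patients respond. The plan offers nothing to set against that reading except two separate confidence intervals.

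**Working it through.** **Inputs**
- Overall power of 84%. It is visible only in the protocol's summary of changes, as the new value ("power of 84% and 95% CIs").
- Two-sided alpha of 0.05 (protocol 9.1).
- 1:1 allocation "until approximately 180 subjects are randomized" (protocol 3.1), so 90 per arm.
- Assumptions: even splits, and the same true effect in both levels. The SHAPS median splits are about even apart from ties. The gender and HAMD-17 proportions are not given.

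**The 84% figure.** It cannot be reproduced independently, because the visible text gives no effect size, SD or dropout rate. It can be inverted:

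overall noncentrality = z(0.975) + z(0.84) = 1.960 + 0.994 = 2.954

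With 90 per arm this implies a standardized effect of 2.954 × √(2/90) = 0.440. With 72 evaluable per arm it would be 0.492. The noncentrality stays at 2.954 in either case, and the rest of the calculation uses only that number.

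**Power in one half.** Noncentrality = 2.954 × √0.5 = 2.089. Power = Φ(2.089 − 1.960) = Φ(0.129) = 0.551; the other tail is negligible.

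**Exactly one half significant.** The halves contain different subjects, so their tests are independent:

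2 × 0.551 × (1 − 0.551) = 0.495

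Both halves are significant with probability 0.304 and neither with probability 0.201. A noncentral-t calculation gives 0.496 for exactly one. By symmetry, the probability that a named half is the only significant one is half of 0.495, or 0.247.

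**Dependence on the true effect (even split)**

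| True effect, relative to design | Overall power | Power per half | Exactly one significant | High-SHAPS only |
|---|---|---|---|---|
| 1.25 | 96% | 74.3% | 38.2% | 19.1% |
| 1 | 84% | 55.1% | 49.5% | 24.7% |
| 0.75 | 60% | 34.7% | 45.3% | 22.7% |
| 0.5 | 31% | 18.1% | 29.7% | 14.8% |
| 0.25 | 11% | 8.2% | 15.0% | 7.5% |
| 0 | 5% | 5.0% | 9.5% | 4.8% |

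The bottom row is 2 × 0.05 × 0.95 = 0.095. It counts significance in either direction.

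**Uneven splits at the design effect.** With share f in one level, its noncentrality is 2.954 × √f. Exactly one level is significant in 50.9% of trials at 60/40 and 55.2% at 70/30.

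**Interaction test.** With a common true effect it rejects 5% of the time, whatever that effect is. At the design effect, only about 10% of trials with one significant and one non-significant half also have an interaction p-value below 0.05 (simulation, 2 million draws).

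**Any of eight p-values with no drug effect.** I simulated 180 subjects, 90 per arm, with four even splits: two unrelated, and two SHAPS splits whose underlying scores correlate 0.6 to 0.9 (an assumption). At least one of the eight p-values fell below 0.05 in 24% to 25% of trials. The pre/post-COVID split is not included.

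**Power of the interaction test.** In an even split, each half's estimate has twice the variance of the overall estimate. Their difference has four times that variance, so its SE is doubled. For a difference between halves as large as the design effect, noncentrality is 2.954 / 2 = 1.477 and power is about 31%.

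**The case against.** The strongest case against is that these are supportive analyses with no consequence written into the plan. No decision rule, claim or selection criterion in the visible text depends on a subgroup p-value. One primary test is designated, and the lack of adjustment elsewhere is stated openly. The repeated MMRM already reports estimates, standard errors and 95% CIs within each level. Because the levels contain different subjects, a reader can form the contrast by hand. An interaction test would be weak at this size, and a non-significant one can mislead too. All of this stands and limits the point to a minor one. It does not explain why the plan should print a p-value for each level and leave the comparison between levels to the reader.

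A reader might infer several stronger things that the documents do not support:
- **That a split result occurs about half the time even if the drug does nothing.** It does not; the figure is then 9.5% per even split. In a proof-of-concept trial a null or smaller effect is a live possibility.
- **That the full 50% is the risk of a spurious high-SHAPS finding.** That pattern is half of it, about 25% at the design effect.
- **That ten levels will be tested.** Main SAP 7.4.6 describes the pre/post-COVID comparison apart from the listed subgroups, so whether addendum 5.2.3 reaches it is unclear. Protocol 9.3.6 treats the matter as an analysis excluding 24 subjects, which is closer to a robustness check.
- **That subgroup results will select patients for a later trial.** No text says so.
- **That an interaction test is certainly absent.** Some SAP text near the subgroup sections is blacked out, so absence can be claimed only for what is visible. The visible statements of the method, in addendum 5.2.3 and main SAP 7.4.4, contain none.

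**Conclusion.** The point holds as a minor one. The addendum moves the subgroup work from description to separate tests, with no visible estimate of the between-level difference.

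The size depends on the true effect. With a common effect and an even split, exactly one level is significant in about 50% of trials at the design effect, about 30% at half of it, and 9.5% with no drug effect. The share stays at 45% to 50% for overall power between 60% and 90%. An interaction test would give a false signal in 5%. With no drug effect, about 24% of trials would show at least one of eight p-values below 0.05.

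These figures rest on the 84% taken from the summary of changes and on even splits for gender and HAMD-17, which the documents do not give. The undisclosed effect size, SD and dropout do not alter the two-level results. The type I error of the primary test is unaffected; the risk is misreading.

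**What to change.** In addendum 5.2.3, replace the separate models with one MMRM per subgroup factor on the whole Efficacy population. Add subgroup, subgroup-by-week, treatment-by-subgroup and treatment-by-subgroup-by-week terms to the primary model. Report the Week 8 treatment-by-subgroup estimate with its 95% CI and p-value, next to the within-level estimates and CIs. State that power for interaction is low and that the analyses are exploratory. Say whether the pre/post-COVID split is covered. As an option, also fit baseline SHAPS as a continuous modifier, since a median cut discards information.

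The cost is a few lines of SAP text and a few model terms, with no new data. The downside is that a wide, non-significant interaction may be taken as evidence of a uniform effect; leading with the interval rather than the p-value limits that.

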5.2.4 Subgroup Analyses of the Secondary Efficacy Endpoints

The secondary efficacy endpoint SHAPS will be summarized using the subgroups described in the main SAP. HAM-A total score will instead be presented by baseline SHAPS Total Score (14 to 56) (< median and \geq median) and SHAPS Original Total Score (0 to 14) (< median and \geq median).

5.3 Safety Evaluation

5.3.1 Vital Signs, Physical Findings, and Other Observations Related to Safety

5.3.1.1 Ophthalmology Examination

The main SAP states "Standard ophthalmologic examination and corneal specular microscopy examination results will be summarized by presenting shift from baseline to end of study results as normal, abnormal not clinically significant, and abnormal clinically significant." This summary will be presented by visit.

Additionally, the subjects who have endothelial dystrophy medical history prior to treatment used for the subgroup analysis will be identified by having a preferred term of "Corneal Dystrophy" collected on the Medical and Psychiatric History Other Than MDD (major depressive disorder) electronic case report form (eCRF) prior to date of first dose of study drug.

DocuSign[•]

Certificate Of Completion		
Envelope Id: B873441E0C1E48ED881DC6068D760 Subject: Complete with DocuSign: BlackThorn_K2-M Source Envelope:)AA4 MDD-201_SAP Addendum_v1.0_06OCT2022.docx	Status: Completed
Document Pages: 9 Certificate Pages: 6 AutoNav: Enabled Envelopeld Stamping: Disabled Time Zone: (UTC-08:00) Pacific Time (US & Canada	Signatures: 5 Initials: 0 a)	Envelope Originator:
Record Tracking		
Status: Original 10/6/2022 10:54:51 AM	Holder:	Location: DocuSign
Signer Events	Signature	Timestamp
Principal Biostatistician Precision for Medicine, Oncology and Rare Disease Security Level: Email, Account Authentication (Required)	Signature Adoption: Pre-selected Style Signature ID: 9E683A07-3C33-4051-A68D-48084B8342E1	Sent: 10/6/2022 10:59:24 AM Viewed: 10/6/2022 12:03:08 PM Signed: 10/6/2022 12:03:43 PM
	With Signing Authentication via DocuSign password With Signing Reasons (on each tab): I approve this document	
Electronic Record and Signature Disclosure: Not Offered via DocuSign		
[name]: Email, Account Authentication (Required)	DocuSigned by: Signer Name: Signing Reason: I approve this document Signing Time: 06-Oct-2022 J 2:25:56 PM PDT C73F6D48471248418A5BB7CF72546EDF Signature Adoption: Pre-selected Style	Sent: 10/6/2022 10:59:24 AM Viewed: 10/6/2022 2:25:43 PM Signed: 10/6/2022 2:27:18 PM
Electronic Record and Signature Disclosure: Accepted: 10/6/2022 2:25:43 PM ID: 44075589-189c-42ba-ad35-181a799bc7c1	Signature ID: C73F6D48-4712-4841-8A5B-B7CF72546EDF Using Signed using mobile With Signing Authentication via DocuSign password With Signing Reasons (on each tab): I approve this document	

3 LIST OF ABBREVIATIONS

Abbreviation	Definition
Ab	antibody
AE	adverse event
AESI	adverse event of special interest
ALT/SGPT	alanine aminotransferase
ANC	absolute neutrophil count
ANCOVA	analysis of covariance
AST/SGOT	aspartate aminotransferase
ATC	Anatomical Therapeutic Chemical
BMI	body mass index
BP	blood pressure
BUN	blood urea nitrogen
C-SSRS	Columbia Suicide Severity Rating Scale
CGI-I	Clinical Global Impression of Improvement
CGI-S	Clinical Global Impression of Severity
CI	confidence interval
СК	creatine kinase
СРК	creatine phosphokinase
COWS	Clinical Opiate Withdrawal Scale
COVID-19	coronavirus disease 2019
CSM	Corneal Specular Microscopy
CSR	clinical study report
CV	coefficient of variation
DSM-5	Diagnostic and Statistical Manual of Mental Disorders Fifth Edition
ECG	electrocardiogram
eCRF	electronic case report form
GGT	gamma-glutamyltransferase
GLMM	generalized linear mixed model
HADS	Hospital Anxiety and Depression Scale
HADS-A	Hospital Anxiety and Depression Scale - Anxiety Subscale
HADS-D	Hospital Anxiety and Depression Scale - Depression Subscale
HAM-A	Hamilton Anxiety Rating Scale
HAMD-17	Hamilton Depression Rating Scale - 17-item Version
HAV-Ab	hepatitis A virus antibody
HBc Ab	hepatitis B core antibody

Table 1List of Abbreviations

Confidential

Abbreviation	Definition
HBs Ag	hepatitis B surface antigen
HC Ab	hepatitis C antibody
HIV	human immunodeficiency virus
HPMC	hydroxypropyl methylcellulose
ICF	informed consent form
ICH	International Council for Harmonisation
IgM	immunoglobulin M
INR	International normalized ratio
IWRS	interactive web-response system
KORA	kappa opioid receptor antagonist
LOCF	last observation carried forward
LS	least-square
MCV	mean cell volume
MCHC	mean cell hemoglobin concentration
MDD	major depressive disorder
MedDRA	Medical Dictionary for Regulatory Activities
MI	multiple imputation
MMRM	mixed-models repeated measures
OD	oculus dextrus
OS	oculus sinister
PC	pre COVID
PCS	potentially clinically significant
POC	proof of concept
РР	Per-Protocol
QD	once daily
QTcB	corrected QT interval using Bazett's correction
QTcF	corrected QT interval using Fridericia's correction
RBC	red blood cells
SAE	serious adverse event
SAP	statistical analysis plan
SD	standard deviation
SDS	Sheehan Disability Scale

Abbreviation	Definition
SE	standard error
SHAPS	Snaith-Hamilton Pleasure Scale
SI	Système International
SIGH-A	Structured Interview Guide for the Hamilton Anxiety Rating Scale
SIGH-D	Structured Interview Guide for the Hamilton Depression Rating
	Scale
SOC	system organ class
TEAE	treatment-emergent adverse event
TESAE	treatment-emergent serious adverse event
THC	delta-9-tetrahydrocannabinol
TSH	thyroid stimulating hormone
ULN	upper limit of normal
WBC	white blood cell
WHODrug	World Health Organization Drug classification

